Administration of entolimod resulted in rapid and substantial dose-related increases in plasma levels of G-CSF and IL-6. IL-8 and IL-10 were also elevated. Plasma cytokine levels typically peaked by 4 hours and decreased to pre-dose levels by 7 to 12 hours after injection. Increases in absolute neutrophil count (ANC) were observed in all dose groups after entolimod administration, peaking by ~7 to 24 hours and returning to pre-dose levels by 5 days (120 hours) after injection. Administration of ibuprofen prior to entolimod dosing appeared to augment the entolimod-mediated increases in plasma concentrations of cytokines (e.g., G-CSF, IL-6, IL-8, IL-10) relative to administration of entolimod alone.

Entolimod administration was associated with unpleasant, but transient and generally mild, adverse effects, which were primarily comprised of elements of a flu-like syndrome (malaise, fatigue, chills, fever, myalgias, and nausea) that are consistent with TLR agonism. As specifically evaluated in the development program, the constitutional components of the flu-like syndrome could be lessened either preemptively or reactively with ibuprofen while still preserving the desired pharmacodynamic activity of entolimod.

Transient increases in white blood cell count (WBC) and ANC and decreases in platelet count and absolute lymphocyte count (ALC) were seen in response to entolimod administration. These changes were considered to be components of the expected mechanism-related activity of entolimod, had no clinical sequelae, and were not considered adverse effects. Administration of entolimod was also associated with transient increases in serum levels of alanine aminotransferase (ALT) and aspartate aminotransferase (AST), without changes in serum levels of alkaline phosphatase (ALP) or bilirubin. Such hepatic transaminase changes are considered consistent with the mechanism of action of entolimod and may result from recruitment of large numbers of natural killer cells to sites of TLR5 activation such as the liver ^[16]. The data from

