1.6.1 Definition of DLT

Reference should be made to the Guidance for Industry Toxicity Grading Scale for Healthy Adult and Adolescent Volunteers Enrolled in Preventive Vaccine Clinical Trials for grading the severity of AEs and laboratory abnormalities where applicable. Based on the known safety profile of entolimod, flu-like symptoms are expected. Decreases in blood pressure, increases in heart rate, hepatic transaminase elevations, hyperglycemia, and hypophosphatemia are expected. DLT will be defined based on the sound clinical judgement of the investigator. DLTs will be considered adverse events and their time and grade severity will be recorded.

These risks and benefits are outlined in the Informed Consent Form and listed in the Investigators Brochure.

2 Study Objectives

Primary Objective

- To evaluate the effect of increasing dose of entolimod on enhancement of the influenza vaccine immunogenicity in the geriatric population (≥ 65 years old).

- To characterize the safety profile of entolimod within the geriatric population (≥ 65 years old) vaccinated against influenza.

Secondary Objectives

- To evaluate the pharmacodynamic effects of entolimod on immunological status, markers of senescence, viscoelasticity of tissue at the injection site, frailty indices and quality of life (QoL).

Exploratory Objectives

- To determine levels of anti-COVID-19 serum-circulating antibodies in a population of confirmed COVID-19 cases
- To determine the rate of the following occurrence in patients that become COVID-19 positive: (i) disease progression requiring hospitalization; (ii) acute respiratory distress syndrome (ARDS); (iii) and 30-day mortality following study drug administration.

3 Study Design

This clinical trial is a randomized, double-blind, placebo-controlled, dose-escalated, single-administration study evaluating the immunogenicity, pharmacodynamics, and safety of entolimod within the geriatric population (≥ 65 years old) vaccinated against influenza. After providing a written informed consent, subjects will undergo screening medical history, physical examination, vital signs, laboratory, and electrocardiogram (ECG) assessments within 28 days prior to study drug administration and influenza vaccination (see figure 2 below).

[figure not shown]

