3.3 Duration of Participation

After consent, for each individual, the duration of participation will be for the length of time required to perform screening plus the 12-month follow-up period after the single-dose administration of entolimod. It is anticipated that the screening will occur within seven days of written content.

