3.5 Secondary Study Endpoints

Pharmacodynamics and Cellular Immune Responses to Influenza Vaccination

- Time to onset and the number of upper-respiratory infections, including (but not limited to) influenza viral infections (as indicated by subject self-reporting)
- Changes in the concentration of circulating plasma cytokines including (but not limited to): IL-6 and G-CSF as pharmacodynamic indicators of entolimod's activity (measured using MSD assay platform)
- Changes to 10 cytokine/chemokine mediators of adaptive immune function (IFN- γ , IL-1 β , IL-2, IL-4, IL-6, IL-8, IL-10, IL-12p70, IL-13 and TNF- α) in PBMC culture supernatants at 0 and 24 hours after influenza (A/H1N1, A/H3N2 and B) viral stimulation as detected by Meso Scale Discovery, V-PLEX Proinflammatory panel human immunoassay kits.
- Changes in the quantification of IFN γ -positive cells as a marker of cell-mediated immunity (CMI) after vaccination using influenza virus-specific IFN- γ ELISPOT assay kits from R&D Systems.

- Changes in frailty indices and quality of life (QoL) of individuals receiving entolimod versus placebo
- Changes in measures of physical function (6-minute walk test, grip strength) and body composition

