6.15 Adverse Events

Adverse event monitoring will be conducted throughout the study for all subjects. The AE and serious adverse event (SAE) reporting period begins at the time of informed consent and continues through study completion. Adverse events will be assessed at every site and remote visit.

The Investigator will follow-up on all AEs observed or reported by the subject up to the end of the reporting period or until follow-up is no longer necessary. The Investigator will follow-up on SAEs until they are considered resolved or the outcome is known.

Definitions, documentation, and reporting of AEs are described in Section 8. Serious adverse events must be reported within 24 hours as described in Section 8.2.

Table S-1. Schedule of Events

PERIOD	Screening Visit	Treatment Visit	Safety Follow-Up		Monthly Follow-Up					
ON-SITE VISIT	1	2	3	4 (remote)	5	6	-	7	-	8
WEEK	-4	0	Day 1	1						
MONTH					1	2	3 to 5 ^[p]	6	7 to 11 ^[p]	12
Visit Window, week(s)	-28 days			± 1 day	± 1 week					
General Eligibility, Safety, and Frailty Assessments										
Eligibility assessment	X									
Written informed consent	X									
MMSE cognitive status assessment	X									
Frailty assessments ^[a]	X						X	X		X
Brief physical examination ^[b]	X		X							
Medical history	X									
Demographic Information	X									
Vital signs/oxygen saturation/Ht/Wt ^[c]	X ^[q]	X ^{[d][q]}	X ^[q]		X ^[q]	X ^[q]		X ^[q]		X ^[q]
12-lead ECG	X		X		X	X		X		X
AE assessment, including respiratory infection assessment	X	X	X	X	X	X	X	X	X	X
Concomitant medications	X	X	X	X	X	X	X	X	X	X
Quality of life (QoL) questionnaire	X		X	X	X	X	X	X	X	X
Study Drug Administration										
Study drug		X								
Laboratory Assessments										
Serum chemistry ^[e]	X		X		X	X		X		X
Hematology ^[f]	X		X		X	X		X		X
Coagulation ^[g]	X		X		X	X		X		X
Serum virology ^[h]	X									
Urinalysis ^[i]	X		X		X	X		X		X
Serum for entolimod-reactive antibodies ^[j]	X		X		X	X		X		X
Plasma for pharmacodynamics ^[k]		X								
Serum for vaccine related antibodies ^[l]		X			X	X		X		X
Peripheral blood mononuclear cells (PBMC) ^[m]		X			X	X				X
COVID-19, PCR [SARS Coronavirus 2, Molecular Detection, PCR (NP)]		X								X
Exploratory Procedures										
SAVE ^[n]		X								
Biomarkers of senescence ^[o]		X			X			X		X
SARS-CoV-2 IgG Ab [SARS Coronavirus 2 IgG Ab, Serum]		X								X

Footnotes
[a] To be collected at screening, baseline, months 2, 6 and 12 (includes questionnaires, physical function testing, and body composition)

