The distribution of antibody titers (A/H1N1, A/H3N2, B) during follow up is anticipated to be skewed based on reporting in prior studies and a log-transformation will be applied to these outcomes. Antibody titers are measured at multiple time points in the first week after treatment, 4 weeks, 2 months, 6 months, and 12 months. A hierarchical mixed-effects regression model will be fit separately for the 3 endpoints, adjusting for the baseline/screening observation of the titer (an analysis of covariance (ANCOVA) approach). The model will include random subject-specific intercepts and model time as discrete. The primary outcome comparison is a contrast analysis of the outcome at 4 weeks comparing each entolimod dose to placebo. As the overall aim of this study is to assess safety and identify potential efficacy of entolimod, especially the dose most likely to succeed in Phase III study, we apply a one-sided test at alpha level 0.15 to each dose comparison (vs. placebo) and antibody titer combination, without multiplicity adjustment. The primary analysis will be conducted using the modified intent-to-treat analysis dataset.

Secondary Hypotheses: Secondary and exploratory endpoints require a variety of standard statistical methods.

Key secondary endpoints include the frailty indices, measures of physical function (6 minute walk test and grip strength), and quality of life (QOL). Frailty indices are measured at 2, 6, and 12 months and QOL measured at each study visit. For these outcomes, linear mixed effects models will assess the relationship between randomized arm and outcomes over time. Discrete times will be considered corresponding to the study visit and secondary analyses may consider continuous linear time (constant slope over time) for changes in the outcome. For these outcomes, the 12 month observation is the primary comparison.

Upper respiratory infections, including influenza, will be recorded over the follow up period. We anticipate the total number of these will be infrequent. Thus, we compare the outcome of any infection (vs. no infection) across randomized arms using a Pearson chi-square test or Fisher's exact test. Secondary approaches may consider analysis of the ordinal count of the number of infections, analyzed using a trend test.

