7.3 Subject Population(s) for Analysis

The primary analysis uses a modified intent-to-treat principle. Patients will be analyzed based on randomized arm using methods described previously. Exploratory analyses will assess whether a differential sex-based response to treatment exists for the primary outcomes and secondary outcomes of FI and QOL, using interaction terms in regression models.

8 Safety and Adverse Events

For safety analyses, AEs will be classified using the Medical Dictionary for Regulatory Activities (MedDRA). The severity of AEs will be graded by the investigator according to the Guidance for Industry Toxicity Grading Scale for Healthy Adult and Adolescent Volunteers Enrolled in Preventive Vaccine Clinical Trials. Concomitant medication use will be coded using the World Health Organization Drug Dictionary (WHODRUG) into Anatomical Therapeutic-Chemical classification (ATC) codes; these data descriptions will particularly focus on supportive medications and care provided in response to any study-study-induced adverse effects and to therapies for GVHD. For ECG assessment of QT intervals, correction by both the Bazett and Fridericia methods will be applied, and the data will be summarized by CTCAE grading categories in terms of absolute QTc and maximal QTc change from baseline.

A safety analysis will be conducted after 20 patients (5 per arm) have been randomized and completed the one-week safety follow-up period. After the last subject has completed their one-week safety follow-up period, there will be a temporary halt in additional participation pending analysis of safety outcomes, anticipated to be no longer than seven days. A safety report will be generated after the 20th patient completes 1 week follow up, summarizing all adverse events overall and by study arm while maintaining blind (groups denoted as A-D in random order). If appropriate, as described below, unblinded and subject-level adverse event data will be provided. Adverse events, both short term (14 days) and long term (through 365 days), will continue to be collected with ongoing monitoring as specified in the Data Safety Monitoring Plan (DSMP).

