For this study, the study treatment follow-up period is defined as (365) days following the last administration of study treatment.

Preexisting Condition

A preexisting condition is one that is present at the start of the study. A preexisting condition should be recorded as an adverse event if the frequency, intensity, or the character of the condition worsens during the study period.

General Physical Examination Findings

At screening, any clinically significant abnormality should be recorded as a preexisting condition. At the end of the study, any new clinically significant findings/abnormalities that meet the definition of an adverse event must also be recorded and documented as an adverse event.

Post-study Adverse Event

All unresolved adverse events should be followed by the sponsor-investigator until the events are resolved, the subject is lost to follow-up, or the adverse event is otherwise explained. At the last scheduled visit, the sponsor-investigator should instruct each subject to report, to the sponsor-investigator, any subsequent event(s) that the subject, or the subject's personal physician, believes might reasonably be related to participation in this study.

Abnormal Laboratory Values

A clinical laboratory abnormality should be documented as an adverse event if it changes from value within the normal range before treatment to one outside and worse than the normal range after treatment. Such changes will prompt a repeat test, telephone call to check the subject's status, a repeat visit, and/or referral to the subject's primary care physician.

Hospitalization, Prolonged Hospitalization or Surgery

Any adverse event that results in hospitalization or prolonged hospitalization should be documented and reported as a serious adverse event unless specifically instructed otherwise in this protocol. Any condition responsible for surgery should be documented as an adverse event if the condition meets the criteria for an adverse event.

Neither the condition, hospitalization, prolonged hospitalization, nor surgery are reported as an adverse event in the following circumstances:

- Hospitalization or prolonged hospitalization for diagnostic or elective surgical procedures for a preexisting condition. Surgery will **not** be reported as an outcome of an adverse event if the purpose of the surgery was elective or diagnostic and the outcome was uneventful.

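### Self-reported respiratory infection is counted from dosing without a case definition, so any excess of flu-like drug reactions in the active arms could be scored as infection

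*Combined protocol and SAP*

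**What the plan says.** **Endpoint.** Section 3.5 lists "Time to onset and the number of upper-respiratory infections, including (but not limited to) influenza viral infections (as indicated by subject self-reporting"). Section 7.2 adds: "Upper respiratory infections, including influenza, will be recorded over the follow up period". The planned comparison is any infection versus none across the randomised arms, by Pearson chi-square or Fisher's exact test. A trend test on the number of infections is optional. Section 7.2 expects few infections but gives no rate.

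**Start of counting.** Section 3.3 refers to "the 12-month follow-up period after the single-dose administration of entolimod", and Section 8.1 says "the study treatment follow-up period is defined as (365) days following the last administration of study treatment". No interval after dosing is set aside. A respiratory infection assessment is listed for Day 0, Day 1 and Day 7 (Sections 6.2 to 6.4). In Table S-1 it shares one row with adverse events: "AE assessment, including respiratory infection assessment".

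**Expected reaction.** Section 1.6.1 states: "Based on the known safety profile of entolimod, flu-like symptoms are expected". Section 1.4.2.1 describes "elements of a flu-like syndrome (malaise, fatigue, chills, fever, myalgias, and nausea) that are consistent with TLR agonism".

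**What is absent.** The plan gives no case definition for an upper respiratory infection, no influenza test of reported episodes, no adjudication, and no rule separating a drug reaction from an infection. PCR is named only for COVID-19.

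**Evidence that reactions may be few.** Section 1.6 says similar doses have not been linked to adverse reactions. Section 1.4.2.4 reports no treatment-related adverse events with 1 µg given alongside tetanus-diphtheria vaccine.

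**The concern.** A subject with fever, chills and myalgia soon after an injection may say that he or she has flu when asked about respiratory infection on Day 1 or Day 7. The endpoint includes influenza and rests on self-report, so nothing in the text stops that answer from counting.

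Randomisation and blinding do not remove the problem if the reaction is more frequent after entolimod than after placebo. The surplus false events then fall in the active arms. The any-infection comparison would be biased against entolimod, and could hide a real reduction or suggest an excess where none exists.

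**Working it through.** The plan states no rate, effect size or power for this endpoint, so there is no figure to reproduce. The check is an illustration.

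**Inputs**
- From the plan: 25 subjects per arm (Section 7.1); binary outcome, any infection versus none (Section 7.2).
- Assumed: placebo risk p = 30%, with 20% and 40% as a range; true risk ratio RR; m, the share of an active arm, in excess of placebo, whose reaction is scored as an infection; a two-sided 5% test, because the plan states no level for this comparison.

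**Formula.** Misreporting is taken as independent of true infection, and placebo misreporting is set to zero so that m is the excess:

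observed active risk = 1 − (1 − p·RR)(1 − m)

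**No true effect (RR = 1), p = 30%**

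| m | Observed active risk | Apparent ratio | Chance of a nominally significant excess, one active arm v placebo |
|---|---|---|---|
| 0% | 1 − 0.70 × 1.00 = 0.300 | 1.00 | 2.7% |
| 5% | 1 − 0.70 × 0.95 = 0.335 | 1.12 | 4.8% |
| 10% | 1 − 0.70 × 0.90 = 0.370 | 1.23 | 8.1% |

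The last column enumerates an uncorrected chi-square test of 25 versus 25 exactly. For a four-arm test, with m of 0%, 5% and 10% in the three active arms, the false-positive rate moves from about 5% to about 7%.

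**Sensitivity to p (RR = 1).** For m = 5% and 10%:
- p = 20%: ratios 0.24/0.20 = 1.20 and 0.28/0.20 = 1.40.
- p = 40%: ratios 0.43/0.40 = 1.07 (1.075 before rounding) and 0.46/0.40 = 1.15.

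The rarer the true infections, the larger the distortion for a given m.

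**A true benefit.** With p = 30% and RR = 0.80, m = 5% gives 1 − 0.76 × 0.95 = 0.278 (ratio 0.93), and m = 10% gives 1 − 0.76 × 0.90 = 0.316 (ratio 1.05). The m that exactly cancels a benefit is 1 − (1 − p)/(1 − p·RR). For RR = 0.70:
- p = 20%: 1 − 0.80/0.86 = 7.0%, or 25 × 0.070 = 1.7 subjects.
- p = 30%: 1 − 0.70/0.79 = 11.4%, or 2.8 subjects.
- p = 40%: 1 − 0.60/0.72 = 16.7%, or 4.2 subjects.

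Roughly two to four misreports in an arm of 25 would therefore erase a 30% reduction.

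**How plausible is m above zero?** The flu-like syndrome in Section 1.4.2.1 comes from two pooled studies of 50 + 100 = 150 subjects. Only 6 + 6 + 6 = 18 of them (12%) received 12 µg or less, and no flu-like rate by dose is given. The reaction-free experience in Section 1.4.2.4 is 1 µg in 25 treated men aged 18 to 40, which says little about 3 or 10 µg at age 65 and over. The documents therefore neither fix m nor exclude zero.

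**The case against.** The strongest reply is that confusion may hardly occur:

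- Section 1.6 attributes the flu-like symptoms to doses 5 to 50 times those planned, and reports no adverse reactions at similar doses.
- The listed syndrome contains no cough, sore throat or nasal symptom, whereas the endpoint is upper respiratory infection.
- Cytokines return to pre-dose levels within 7 to 12 hours (Section 1.4.2.1). Subjects are observed for at least six hours and examined on Day 1, and each adverse event is graded for relationship to the drug. Many reactions would be recorded as such.
- The respiratory assessment form is not in the documents and may already ask about symptoms. The Day 0 assessment is not stated to be after dosing.

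All of this stands as a reason to expect a small effect. It does not supply the missing definition, and Section 1.6.1 still says that flu-like symptoms are expected.

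A reader might also infer three stronger points, which the documents do not support:

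1. *Misreporting occurs only in active arms and rises with dose.* Every arm receives high-dose influenza vaccine (Section 3), so placebo subjects can misreport too. Section 1.4.2.1 finds no clear dose-related pattern of adverse effects, although it allows that body weight may have obscured one. Section 1.4.2.5 sees little evidence of a dose response in total event frequencies among older patients.
2. *A planned time-to-onset analysis would be distorted.* Time to onset is a declared endpoint, but Section 7.2 plans no time-to-event analysis.
3. *Early infections should leave the main count because antibody cannot yet have acted.* The background in Section 1.1 also invokes innate activation and an antiviral effect of TLR5 stimulation, which could act early. The 14-day boundary in Section 8 ("Adverse events, both short term (14 days) and long term (through 365 days") is an adverse-event category and was not written for infections.

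**Conclusion.** The point holds as a gap in ascertainment. Self-reported infection, counted from dosing without a case definition, leaves room for differential misclassification against entolimod if active arms have more flu-like reactions than placebo.

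The bias is possible, not demonstrated. The apparent ratios of 1.00, 1.12 and 1.23 depend on an assumed 30% placebo risk, no true effect and assumed excess misreporting of 0%, 5% and 10%. In an arm of 25, 5% to 10% is one to three people (25 × 0.05 = 1.25; 25 × 0.10 = 2.5). The effect on the chance of a false signal is modest.

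The endpoint is secondary, and the primary HAI comparison is unaffected. This is a cheap improvement to a declared endpoint; it does not threaten the trial's main conclusion.

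**What to change.** In Sections 3.5 and 7.2:

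1. Count a self-reported upper respiratory infection only if at least one localising respiratory symptom is recorded (for example cough, sore throat or nasal symptoms). Add one item for this to the existing respiratory assessment if it is not already there.
2. Keep counting from dosing in the main analysis, so that all randomised follow-up is used.
3. Tabulate early post-dose reports separately by arm, with the window fixed in advance (for example Days 0–7 or Days 0–14).
4. Pre-specify a sensitivity analysis that excludes episodes with onset in that window.

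**Cost.** One form item, a little extra analysis, and possibly a few true infections missed because they show only systemic symptoms. The sensitivity analysis alone gives up early follow-up: 7/365 = 1.9% or 14/365 = 3.8% of the year. No dose, visit or clinical rule changes.
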